**April 14, 2018**

# **Efficacy Study of Yi-Zhi-An-Shen Granules for Older Adults with Amnestic Mild Cognitive Impairment**

## **Study Protocol with SAP**

### **1. Objectives**

The primary objective of this study is to evaluate the efficacy and safety of Yi-Zhi-An-Shen Granules (YZASG) in optimizing cognitive performance over time in elderly individuals with amnestic mild cognitive impairment (aMCI). Secondly, the investigators intend to assess whether YZASG can improve sleep quality among aMCI patients. Finally, participants' fecal genomic DNA will be extracted to analyze the gut microbial differences between individuals with aMCI and ones with normal cognition.

### **2. Design**

This study is a randomized, double-blind, placebo-controlled trial with 16-week intervention and 18-month follow-up assessment. The design met the principles of the Declaration of *Helsinki*, and was approved by the Ethics Committee of Teaching Hospital of Chengdu University of Traditional Chinese Medicine. Then signed informed consents will be obtained from each participant.

The enrolled participants will be randomly assigned into the YZAS group or the placebo group with the allocation ratio of 1:1 using the statistical package. The unique code will be assigned to each newly enrolled participant and preserved in the trial management board. A statistician expert will act as the coder and be shielded from subject recruitment.

### **3. Methods**

#### **3.1 Participants**

The investigators anticipate recruiting 80 participants from Teaching hospital of Chengdu University of Traditional Chinese Medicine, community, and nursing homes. All patients will undergo standard medical examination and neuropsychological testing to ensure correct diagnosis of aMCI.

The inclusion criteria are (1) subject has assigned informed consent to participate in the study and continues to give willing consent for participation; (2) age from 60 to 85 years with a diagnosis of aMCI; (3) educational level of at least 6 years; (4) availability of a "study partner" who can assist in completing rating scales for the duration of the study; (5) cognitive complaints reported by the subject and confirmed by the "study partner"; (6) clinical Dementia Rating (CDR) global score of 0.5, and memory item score of 0.5; (7) mini-mental state examination (MMSE) score of 24-30; (8) Diagnostic and Statistical Manual of Mental Disorders, Version 5 (DSM-V) criteria of dementia not fulfilled

The exclusion criteria are as follows: (1) has been previously enrolled in this study and received the investigational product; (2) has received an investigational product within 30 days prior to screening; (3) has received disease-modifying therapy; (4) has a known allergy to the study drug or any of its constituents; (5) has a history of alcohol abuse or alcohol dependency in the 3 years prior to study entry, or is an alcoholic or drug addict, as determined by the investigator; (6) has ongoing clinically significant (as judged by the investigator), metabolic or any other disease that could currently cause impaired memory (e.g., untreated thyroid disease, vitamin or other nutritional deficiencies, chronic kidney, or liver disease); (7) memory impairment that can be attributed to a disease or condition other than an early phase neurodegenerative syndrome; (8) has a parkinsonian movement disorder; (9) use of psychoactive medications that would affect the subject's ability to reliably perform neurocognitive testing or create uncertainty in distinguishing between the effects of the psychoactive medication and the subject's underlying cognitive impairment (e.g., benzodiazepines, sedatives, antipsychotics); (10) with history of major recurrent depressive disorder (DSM-V) within the last 5 years prior to screening; (11) has a brain tumor or other

intracranial lesion, a disturbance of cerebral spinal fluid circulation (e.g., normal pressure hydrocephalus), and/or a significant history of head trauma or brain surgery; (12) has signs of major cerebrovascular disease, with score of modified Hachinski Ischemia Score (mHIS) at more than 4, or as verified by medical history and/or brain MRI or CT; (13) has severe visual or hearing impairments that cannot cooperate with examinations; (14) has severe digestive system diseases; (15) has received antibiotics within 60 days prior to screening.

Handling of withdrawal and dropout: (1) Voluntarily withdrawal, (2) loss of follow-up, (3) poor compliance and presence of severe adverse effects, (4) revealing and uncovering blind in urgency, (5) misdiagnosis, (6) using forbidden drugs or treatments in the course of the trial, (7) taking no medication during the trial, (8) no evaluable records after medication. Reasons for withdrawing participants will be recorded in CRFs, and the last data will be included in data analysis.

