### **3.3 Outcomes**

#### **3.3.1 Primary outcome**

Cognitive decline is measured using the Chinese version of the Alzheimer Disease Assessment Scale-Cognitive subscale (ADAS-cog11). The total possible score is 70. A score increase indicates greater severity of impairment. The specific hypothesis is that the change from baseline to endpoint will be significantly less than that for placebo.

The ADAS-cog will be assessed at baseline (before intervention), at 16 weeks (the end of intervention) and 6, 12, and 18 months after intervention.

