### **4.2 Statistic analysis**

Analysis will be conducted by a statistician of the National Clinical Trial Center of Chinese Medicine (Chengdu, China), who will be blinded to the whole trial and using SAS 9.2 software (Cary, NC, USA) and SPSS 19.0 software (IBM, NY, USA).

Unless otherwise specified, all mechanism, efficacy and safety analyses will be strictly conducted according to the intention-to-treat (ITT) principle and the full analysis set (FAS) population, the per-protocol set (PPS) population and the safety set (SS) population. Missing values will be replaced by the last observation carried forward (LOCF) method. ADAS-cog (including its monomial item) changes from baseline and the secondary outcomes will be assessed using an analysis of covariance with treatment groups as factors and baseline values as covariates. Standardized mean

differences will be used to express effect sizes in SD. The baseline homogeneity of the baseline characteristics between the two groups will be analyzed with Fisher's exact test, or  $\chi^2$  test for categorical measures and with the *t* test or Wilcoxon rank-sum test for continuous measures. The statistical significance is defined as a one-sided P-value of <0.05 and 95% confidence interval.

For the gut microbiome analysis, sequenced data will be interpreted using the bioinformatics tools programmed in the Ion Reporter software. QIIME algorithms will determine the bacterial diversity within a sample ( $\alpha$  diversity) and among all the samples ( $\beta$  diversity). Additionally, multivariate data analysis with principal component analysis on the diversity indexes and comparisons of genus and species level data will be performed to reveal differences in the microbial composition between individuals with normal cognition and ones with aMCI. The Benjamini–Hochberg false discovery rate adjustment will be used to account for the number of taxa tested in each comparison.

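### Section 3.1 does not separate stopping study treatment from leaving the study, so the strict ITT analysis rests on carried-forward scores for withdrawn participants

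*Combined protocol and SAP*

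**What the plan says.** Section 3.1, in the paragraph on handling withdrawal and dropout, gives eight reasons. The first two are voluntary withdrawal and loss to follow-up. The next four are "3) poor compliance and presence of severe adverse effects, (4) revealing and uncovering blind in urgency, (5) misdiagnosis, (6) using forbidden drugs or treatments". The last two are "7) taking no medication during the trial, (8) no evaluable records after medication". The paragraph ends: "Reasons for withdrawing participants will be recorded in CRFs, and the last data will be included in data analysis".

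Section 4.2 describes the analyses in these words: "will be strictly conducted according to the intention-to-treat (ITT) principle and the full analysis set (FAS) population, the per-protocol set (PPS) population". It also names a safety set. None of these sets is defined. On gaps it says: "Missing values will be replaced by the last observation carried forward (LOCF) method".

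Section 3.3.1 sets the primary outcome schedule: "The ADAS-cog will be assessed at baseline (before intervention), at 16 weeks (the end of intervention) and 6, 12, and 18 months after intervention". Its hypothesis concerns change from baseline to the endpoint, with no visit named. Section 3.3.2 adds a week-8 visit for all questionnaires and does not make clear whether that includes the ADAS-cog.

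No section distinguishes a participant who stops the granules from one who leaves the study, and none says whether a withdrawn participant is assessed again.

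**The concern.** An ITT comparison needs outcomes at the scheduled visits from everyone randomized, including those who stop treatment, take something else or are unblinded. Several listed reasons arise after randomization and can depend on the arm or on the course of the disease. Severe adverse effects may be more frequent on one arm. A participant who is declining may start a forbidden treatment, and the off-treatment follow-up of 18 months leaves ample time for that.

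If such a participant is not seen again, the last score stands in for all later visits. In a condition expected to worsen, an early score flatters the participant, and the arm with more or earlier withdrawals gains. Active treatment could then look beneficial because more people left it, or a real benefit could be hidden in the reverse case.

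This is a data-collection question as well as an analysis question. A mixed model or multiple imputation would replace the frozen score with a model-based one, but neither recovers a score that was never taken.

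**Working it through.** **1. The plan's own figure.** Section 4.1 goes from 33 evaluable to 40 enrolled per arm with at most 20% dropout. 33 × 1.20 = 39.6, so 40. The usual form, 33 / (1 − 0.20) = 41.25, gives 42. The point does not depend on this figure. It matters only because 20% is the sole withdrawal rate in the documents (8 of 40 per arm), with no split by arm or by reason.

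**2. The passages together.** Section 3.1 uses the last data of withdrawn participants. Section 4.2 fills missing values by LOCF. The two agree with each other, and withdrawn participants stay in the analysis. What is absent is any provision for observing them later. Under the ADAS-cog schedule in 3.3.1, anyone withdrawn before week 16 has only a baseline score, so the carried-forward change is zero at every later visit. If the ADAS-cog is also done at week 8, some would carry that value instead and the bias would be smaller.

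**3. Formula.** With no true effect, let both arms have mean change m(t) at the analysed visit and mean change m(L) at the last score carried. With withdrawn shares p_T (active) and p_C (placebo):

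bias = (p_C − p_T) × [m(t) − m(L)], negative values favouring active.

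**4. Assumed inputs (none from the documents except 40 per arm, the visit schedule, the ANCOVA and one-sided 0.05).** Worsening 2 points per year, slope SD 2, visit error SD 2; baseline mean 10, SD 4; withdrawal unrelated to a participant's own slope; last score equally likely to come from any earlier ADAS-cog visit; every withdrawal recoverable by continued assessment.

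Visit times in years: baseline 0; week 16 = 16/52 = 0.31; then 0.81, 1.31 and 1.81 (about 21.7 months).

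**5. Results by arithmetic, 30% active and 10% placebo.**
- 18 months after intervention: mean time of last score (0 + 0.31 + 0.81 + 1.31)/4 = 0.61. Lost worsening 2 × (1.81 − 0.61) = 2.40 points. Bias = −0.20 × 2.40 = −0.48.
- Same visit, all withdrawals before week 16: −0.20 × 2 × 1.81 = −0.72.
- Same visit, all withdrawals after week 16: mean time (0.31 + 0.81 + 1.31)/3 = 0.81. Bias = −0.20 × 2 × 1.00 = −0.40.
- Week 16, all withdrawals before it: −0.20 × 2 × 0.31 = −0.12.

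**6. Simulation of the ANCOVA under the same inputs, no true effect.**

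| Withdrawn, active / placebo | Visit | Bias (points) | One-sided error |
|---|---|---|---|
| 30% / 10% | 18 months | −0.46 to −0.49 | about 12% |
| 25% / 15% | 18 months | −0.23 to −0.26 | about 8% |
| 10% / 30% | 18 months | +0.48 to +0.49 | 1.5% |
| 30% / 10%, all before week 16 | 18 months | −0.72 | about 18% |
| 30% / 10%, all after week 16 | 18 months | −0.40 | about 10% |
| 30% / 10% | Week 16 | −0.12 to −0.14 | about 8% |
| Assessments continued | 18 months | about 0 | about 5% |

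Ranges are across separate runs, some with a slightly different assumed baseline SD. At week 16 the arithmetic value is −0.12.

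**7. A second check within the 20% ceiling.** Take change-score SD = 1, baseline carried forward, 20% active and 5% placebo withdrawn, and assumed declines of 0.25, 0.5 and 1.0 SD. The bias is −0.15 × decline = −0.04, −0.08 and −0.15 SD, with one-sided error 7.3%, 9.9% and 17.1%. With the shares reversed the bias is +0.04, +0.08 and +0.15 SD, and the error 3.5%, 2.2% and 1.1%.

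**The case against.** Five stronger readings are tempting, and the documents do not support them.

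- *Visits stop on withdrawal.* The text never says so. It is the natural inference, because an instruction to use the last data has little purpose if later scores exist, but it remains an inference.
- *The withdrawal rule contradicts ITT.* Nobody is removed from the analysis set by these events, since the last value is kept. The tension is with ITT follow-up and observed outcomes, and it comes from silence in the plan.
- *Poor compliance alone triggers withdrawal.* Item (3) joins poor compliance and severe adverse effects with *and*, so this is uncertain.
- *Month 18 is the primary result.* Section 3.3.1 names only an endpoint. At week 16 the illustrative bias is about a quarter to a third of that at 18 months.
- *Equal withdrawal always dilutes the effect.* That fits a benefit that grows with time. If a week-16 benefit faded after the granules stopped, carrying week-16 scores forward would inflate the later difference.

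Two objections to the size also stand. The 30% / 10% split has no source in the plan, and its 30% exceeds the 20% maximum dropout. The simulation also treats every withdrawal as recoverable, whereas the list includes voluntary withdrawal and loss to follow-up, so only an unknown share of the bias can be removed. All the figures are produced through LOCF, so they must not be added to a separate criticism of LOCF.

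None of this removes the gap. A plan that says "will be strictly conducted according to the intention-to-treat (ITT) principle" should say how outcomes are obtained after treatment stops.

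**Conclusion.** The point holds in limited form and should be acted on. Section 3.1 does not separate treatment discontinuation from study withdrawal, and no section plans assessments after withdrawal, so the ITT results rest on carried-forward scores for these participants. Unequal withdrawal can then bias the ADAS-cog comparison either way.

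The size is illustrative. The false benefit of about 0.5 points (error about 12%) at 18 months and 0.12 to 0.14 points (about 8%) at week 16 requires the assumed worsening, a 20-percentage-point imbalance and full recoverability. With equal withdrawal and no true effect the bias is zero. If scores improved over time, for instance through practice, the sign would reverse. The gap itself needs none of these assumptions.

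**What to change.** Leave the rules on stopping the granules as they are. In 3.1, separate stopping study treatment from leaving the study. State that every randomized participant who has not withdrawn consent continues the already scheduled week-16 and 6-, 12- and 18-month assessments, whatever the compliance, other treatment, unblinding or revised diagnosis. State that these observed scores enter the ITT/FAS analysis.

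In 4.2, define the FAS, PPS and safety set. Use the adherence, forbidden-treatment, unblinding and misdiagnosis items only to define exclusion from the PPS. Voluntary withdrawal and loss to follow-up should not serve that purpose. Record the reason and date for stopping treatment separately from those for leaving the study. Reconcile 3.3.1 and 3.3.2 on whether the ADAS-cog is done at week 8.

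The cost is protocol wording and some effort to keep off-treatment participants attending. No visits or participants are added. Data lost through withdrawn consent or loss to follow-up are not recovered, and the choice of LOCF for the remaining gaps is a separate matter.

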### **3.2 Interventions**

Besides receiving the same basic treatment, including health education, moderate aerobic exercise (30-60 minutes per day) and general nutritional support, participants assigned to the YZAS group will take Yi-Zhi-An-Shen granule, which is composed of *YiZhiRen* (*Alpinia oxyphylla* Miq.) - 5g, *SanQi* (*Panax notoginseng*) - 3g, *ChuanXiong* (*Ligusticum chuanxiong* hort) - 10g, *ZhiZi* (*Gardenia jasminoides* Ellis) - 10g, *YuJin* (*Curcuma longa* L.) - 10g, *DanZhuYe* (*Lophatherum gracile*) - 10g, while ones in the placebo group will take placebo made from starch which appears the same shape, color, smell, taste, texture package and Lot Number. Participants will be instructed to dissolve granules into 100ml of boiled water and to take the solution orally between 30°C to 37 °C three times daily for 16 weeks. Each granule is prepared by Sichuan Neo-green Pharmaceutical Technology Development Co., Ltd, Sichuan China according to the standards of Good Manufactory Practice (GMP).

80% to 120% of drug usages are eligible for protocol plan. The package, drug name, function and indication, usage and dosage, storage condition, valid period and name

of the manufacturer will be marked and a tag indicating 'trial use' will be attached. Drugs must be kept in the appropriate temperature in a dry, cool and shady place. Drug administrators should return unused drugs to estimate participant compliance and record these in the CRFs.

### **3.3 Outcomes**

#### **3.3.1 Primary outcome**

Cognitive decline is measured using the Chinese version of the Alzheimer Disease Assessment Scale-Cognitive subscale (ADAS-cog11). The total possible score is 70. A score increase indicates greater severity of impairment. The specific hypothesis is that the change from baseline to endpoint will be significantly less than that for placebo.

The ADAS-cog will be assessed at baseline (before intervention), at 16 weeks (the end of intervention) and 6, 12, and 18 months after intervention.

#### **3.3.2 Secondary outcome**

Secondary measures includes the MMSE, MoCA (Changsha Version), CDR, PSQI, ADLs, and gut microbiome.

- The MMSE is an 11-question measure that tests five areas of cognitive function (orientation, registration, attention and calculation, recall, and language). The maximum score is 30 and a score below 24 is considered abnormal for dementia screening.
- The MoCA (Changsha Version) will also be used to evaluate general cognitive function, as it contains visuospatial processing and organizational capability which can make up for the shortcoming of the MMSE. The total score for it is 30, with a higher number indicating a more intact cognitive function. Meanwhile, the MoCA has been shown to be a promising tool to detect MCI and early AD.
- The CDR will be used as an assistant evaluation for patients' dementia severity, which scored 0-3, with higher scores indicating more severity. It is a semi-structured interview performed with the patient and caregiver (informant),

characterizing six domains of cognitive and functional performance. The CDR sum of boxes (CDR-SB) scored 0-18, will also be applied to assess patients' cognitive status, with higher scores indicating worse functioning.

- The Pittsburgh Sleep Quality Index (PSQI) will be used to assess participants' comprehensive quality of sleep, which involves sleep quality, sleep duration, sleep efficiency, sleep disorders, daytime dysfunction, sleeping aids, etc. The total score for it is 21, with a higher score indicating a worse sleep quality.
- ADLs will be assessed including basic activities of daily living (BADL) and instrumental activities of daily living (IADL). An individual's BADL will be evaluated mainly by the subjects' performance from the perspectives of bathing, dressing, grooming, initiation, toileting and feeding, with six items and a sum of scores ranging from 0 (normal) to 24 (complete dependence on others). And modified Lawton Instrumental Activities of Daily Living Scale will be used to measure the IADL of a subject, with eight items and a sum of scores ranging from 0 (normal) to 32 (complete dependence on others).

These clinical tests will be administrated by a trained, certified clinician or rater experienced in the assessment of patients with cognitive deficits. And the rater who will conduct the CDR for a patient cannot complete any other rating scales for the same patient, and will be blinded to the results of all other neuropsychological scales. All the questionnaires will be assessed at baseline (before intervention), at 8 and 16 weeks (during intervention) and 6, 12, and 18 months after intervention.

- Fecal genomic DNA will be extracted from frozen stools using QIAamp DNA mini stool kit (Qiagen, Hiden, Germany), obtained from the patients with aMCI and 15-20 participants with normal cognition at baseline. After PCR amplification, DNA fragments will be sequenced on an Illumina HiSeq 2500 instrument and an Illumina HiSeq X instrument for 16SrDNA and metagenomics analyses respectively at Biomarker Technologies Co, Ltd (Beijing, China) to analyze the differences in gut microbiome between patients with aMCI and individuals with normal cognition.

When it is available, the investigators will also assess the change in gut microbiome between the treatment group and the placebo group after the intervention of YZASG in the same way.

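### The comparison of gut microbiome between aMCI and normal cognition has no safeguard against confounding: age, digestive-disease and antibiotic limits are stated only for patients, and no adjustment is named

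*Combined protocol and SAP*

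**What the plan says.** - **Objective (section 1).** The third aim is to "analyze the gut microbial differences between individuals with aMCI and ones with normal cognition".
- **Patients (section 3.1).** "The investigators anticipate recruiting 80 participants", from the hospital, the community and nursing homes. The age limit is part of the diagnostic criterion: "age from 60 to 85 years with a diagnosis of aMCI". Exclusions 14 and 15 read: "14) has severe digestive system diseases; (15) has received antibiotics within 60 days prior to screening".
- **Controls (section 3.3.2).** Stool DNA is "obtained from the patients with aMCI and 15-20 participants with normal cognition at baseline". Section 3.3.2 gives no age range, health or medication criterion, recruitment source or matching for the controls, and no other section does.
- **Analysis (section 4.2).** Alpha and beta diversity, principal component analysis, and "comparisons of genus and species level data will be performed to reveal differences in the microbial composition", with Benjamini-Hochberg adjustment for the number of taxa. No covariate is named for this comparison.

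**The concern.** Controls are not randomised, so comparability with the patients has to come from how they are selected or how the data are analysed. The plan provides neither. Recent antibiotics, severe digestive disease and age could plausibly affect stool microbiota; all three are limited among patients and left open among controls. If control volunteers were younger, or some had taken antibiotics recently, the resulting difference would enter the taxon list as a difference between aMCI and normal cognition. A reader could not separate the two.

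It would also be hard to repair later. If ages or antibiotic histories barely overlap between the groups, no model can adjust for them. The plan does not say that these facts will be recorded for controls at all.

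**Working it through.** **1. Could the eligibility list in section 3.1 cover the controls by default?** Not as a whole. Inclusion requires an aMCI diagnosis and "clinical Dementia Rating (CDR) global score of 0.5, and memory item score of 0.5", which people enrolled as cognitively normal are not expected to meet. The age limit sits inside the aMCI criterion. The list therefore describes trial patients, and no second list exists.

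**2. Does anything in section 4.2 adjust for confounding?**
- Benjamini-Hochberg controls the false discovery rate over many tests. It takes each p-value as valid and does not correct a shifted group mean.
- The analysis of covariance uses treatment group as factor and the baseline value as covariate. Neither applies to a baseline contrast of patients with untreated controls.
- The baseline homogeneity tests concern the two groups, in context the randomised arms. Testing for imbalance would not adjust for it in any case.

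**3. Is there a plan figure to reproduce?** No. The 15-20 controls come without an effect size, SD or power, so what follows is illustration under assumed values.

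**4. One unadjusted test (for example, one alpha diversity index).** Inputs from the plan: 80 patients, 15 or 20 controls. Assumed: no true cognition effect, confounding bias *b* in SD units, two-sided 5% test.
- Standard error in SD units = √(1/80 + 1/n): 0.281 for n = 15 and 0.250 for n = 20.
- Noncentrality = *b*/SE. At *b* = 0.3 this is 0.3/0.281 = 1.07 and 0.3/0.250 = 1.20.
- Rejection probability from the noncentral t distribution (93 and 98 degrees of freedom):

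| Bias (SD) | 15 controls | 20 controls |
|---|---|---|
| 0.1 | 6.4% | 6.8% |
| 0.2 | 10.8% | 12.4% |
| 0.3 | 18.4% | 22.1% |
| 0.4 | 29.1% | 35.4% |

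One route to such a bias: if 10-30% of controls and no patients had recent antibiotics, and exposure moved the index by 0.5-1.0 SD, the bias would be 0.10 × 0.5 = 0.05 SD up to 0.30 × 1.0 = 0.30 SD. These prevalences and effects are assumptions.

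**5. Taxa, with the planned Benjamini-Hochberg step.** The single-test rates above do not apply to taxa. By simulation with 100 independent normal taxa, 20-100% of them shifted by 0.3 SD, two-sided at 5%, over 15 and 20 controls:
- rejection per shifted taxon: about 1-3%;
- at least one false taxon: roughly 17-75%, against 5% if nothing is shifted.

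At 0.4 SD, rejection per shifted taxon is about 2-13%.

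**The case against.** The strongest reply is that this is silence, not a decision. Section 3.3.2 does not say that controls are unrestricted, and section 4.2 does not say that the tests will be unadjusted; it names no test or model at all. The investigators may have meant the exclusions to cover everyone who gives stool. That is fair, and it limits the claim: the plan permits the groups to differ but does not make them differ. A reader might infer that the groups will necessarily be unlike; the documents do not support that. The point still stands, because someone following the text would have no instruction to restrict, match or adjust.

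Second, the plan gives no reason for its patient criteria. Only the antibiotic exclusion clearly suggests a microbiome purpose; the digestive exclusion could equally relate to an oral product, and the age range to a trial in older adults. So it cannot be said that the plan itself recognises all three as confounders. Their relevance is a judgement made here.

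Third, it is tempting to quote the 18-22% rejection at 0.3 SD as the false-positive rate per taxon. It is not: Benjamini-Hochberg lowers that to about 1-3%. The single-test rate is relevant only to diversity indices, which the stated taxon-level adjustment does not cover.

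Fourth, the plan speaks of analysing and revealing differences; it makes no causal claim and promises no microbial signature of aMCI. That is correct, and the stakes are stated here accordingly.

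**Conclusion.** The concern holds for the comparison of aMCI with normal cognition only. As written, it has no protection against confounding by age, antibiotics or digestive disease, either in control selection or in analysis. The direction and size of any bias cannot be determined from the documents. The illustration rests on assumed shifts, independent normal taxa and a two-sided level. The two-sided level is itself a choice: section 4.2 sets a one-sided 0.05 but gives no direction for taxa. Under those assumptions any one shifted taxon is seldom declared, yet at least one false finding in the list is quite possible.

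A reader might extend this to the trial's main results. That would be wrong: the ADAS-cog comparison, the other randomised secondary outcomes and the YZASG-versus-placebo change in microbiome do not use these controls.

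**What to change.** **Section 3.3.2.** Require controls to be aged 60-85 and to meet exclusions 14 and 15. Frequency-match them to the aMCI group on age band and sex, and draw them where possible from the same settings. Record age, sex and antibiotic history for each control.

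**Section 4.2.** Compare alpha diversity and taxa by regression on group plus age and sex, and apply Benjamini-Hochberg to the adjusted taxon p-values. Ordinary regression does not fit between-sample distances, so test beta diversity with a covariate-adjusted distance-based method, such as PERMANOVA with age and sex. Keep the principal component analysis descriptive.

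Recruitment setting should not be a mandatory covariate. With three settings, 15-20 controls average only 15/3 = 5 to 20/3 ≈ 7 per setting, so the cells would be sparse.

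**Cost.** Changes to protocol and SAP wording, with the same number of controls. Control recruitment may be slightly slower, and the models lose a few degrees of freedom. If the exclusions were always meant to cover controls, saying so takes one sentence; the age range, matching and adjustment would still need to be added.
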